## Project: REACH UP!

### Statistical Analysis Plan

This study was designed as a small pilot study with its purpose to discern the means and SD between the groups to determine the appropriate effect size for future work. The pilot study size was set at 12 children for the control group and 12 children for the intervention group. Recruitment occurred at the day of the child's scheduled procedure and participants were randomized via a computer algorithm varying by block sizes of 2 and 4 to blind the investigator at the time of consent.

Analysis included comparison of time points as related to scores on the mYPAS-SF, with group 1 time points (anxiety scores) compared to group 2 time points (anxiety scores). The comparison was desired to see if there was an effect on the scores with the introduction of the iPad (intervention). Means and SD of each time point were calculated and a t test was used to analyze the two groups and then correlate within and between the groups. To discern effect size, the Cohen's d calculation was used.

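### Minor refinement: the effect size meant for future work is Cohen's d with no small-sample correction mentioned; at 12 per arm Hedges' g removes an average overstatement of about 3.6%

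*Combined protocol and SAP*

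**What the plan says.** All of the relevant text is in the Statistical Analysis Plan. The study is described as a small pilot with "its purpose to discern the means and SD between the groups to determine the appropriate effect size for future work". On size: "The pilot study size was set at 12 children for the control group and 12 children for the intervention group". On the comparison of mYPAS-SF scores: "Means and SD of each time point were calculated and a t test was used to analyze the two groups", followed by correlations within and between the groups. On the effect size there is one sentence: "To discern effect size, the Cohen's d calculation was used".

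The plan does not say which SD is the divisor, which of the three assessments (T1, T2 or T3 in the Script) supplies d, or whether d is between groups or within a group. It also does not mention a small-sample correction or a confidence interval, or say how d would become a sample size.

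**The concern.** Cohen's d divides a mean difference by an estimated SD. In small samples the reciprocal of the estimated SD is, on average, larger than the reciprocal of the true SD, so the expected value of d lies further from zero than the true standardized effect. A confidence interval around d shows its imprecision but does not move the point estimate.

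The estimate is intended for planning. Required sample size varies as 1/d², so an effect size that is too large on average leads towards a follow-on trial that is too small. The corrected statistic has its own usual name, Hedges' g. A plan that names only Cohen's d is therefore most naturally read as using the uncorrected one.

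**Working it through.** **Nothing to reproduce.** The 12 per arm is set without a calculation, so the plan has no figure of its own to check.

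**Inputs from the plan.** 12 children per arm; Cohen's d as the effect size; future work as its use.

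**Assumptions, because the plan is silent.** Between-group d with pooled SD; all 24 children analysed; normal scores with equal variances; future trial at a two-sided 5% level with 80% power; true d from 0.3 to 0.8.

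**Step 1: correction factor.** Degrees of freedom m = 12 + 12 − 2 = 22.
- Exact: J = Γ(m/2) / [√(m/2) × Γ((m−1)/2)] = Γ(11) / [√11 × Γ(10.5)] = 0.9655.
- Approximate: J = 1 − 3/(4 × 22 − 1) = 1 − 3/87 = 0.9655.

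**Step 2: average bias.** The expected d is (true effect)/J, and 1/J = 1.036, so d is 3.6% too large on average. At a true d of 0.5 the expected d is 0.5/0.9655 = 0.518, a bias of 0.018. At a true effect of zero the bias is zero.

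**Step 3: sample size at the expected d.** The ratio of planned to needed size is J² = 0.932, a shortfall of 6.8%. From the noncentral t:

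| True d | Needed per arm | Planned per arm at expected d | Power at planned size |
|---|---|---|---|
| 0.3 | 176 | 164 | 77.3% |
| 0.5 | 64 | 60 | 77.5% |
| 0.8 | 26 | 24 | 77.4% |

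**Step 4: size relative to noise.** At 12 per arm and a true d of 0.5:
- The sampling SD of d is about 0.44, so the bias is 0.018/0.44, about 4% of it.
- The central 95% of d values runs from about −0.31 to 1.41.
- Putting the observed d (either sign) into the sample-size formula gives an interquartile range of about 25 to 223 per arm.
- The chance that the resulting trial is smaller than needed is about 51% with d and 50% with g. The chance that it is under half the needed size is about 32% and 30%.

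**Step 5: d against g as estimators, true d 0.5.**
- Mean: 0.518 for d, 0.500 for g.
- Mean squared error: 0.190 for d, 0.177 for g, a reduction of (0.190 − 0.177)/0.190, about 7%.
- Median: about 0.506 for d, 0.488 for g. By this measure d is the closer of the two.

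**Step 6: if the assumptions differ.** With 10 analysed per arm (18 df) the bias is 4.4% and the shortfall 8.3%. With one group's SD as divisor, or a within-group change (11 df), they are 7.5% and 13.5%.

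**The case against.** The strongest reply is that imprecision dwarfs this bias. An effect size from 12 per arm can fall almost anywhere between slightly harmful and very large, and multiplying it by 0.9655 changes little. The figures in Step 4 bear this out. The correction does not rescue a sample size based on one small pilot, and the uncertainty about which assessment supplies d would remain.

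Three stronger readings are tempting, and none is supported.
- A reader might infer that d always overstates the effect. It does so only on average: at a true d of 0.5 about 51% of pilots give a d above the truth.
- A reader might infer that any trial planned from this pilot will be 7% too small. That figure applies when the expected d is put into the formula; a real pilot supplies one d, which can be far off in either direction.
- A reader might infer that the effect size is the pilot's only product. The plan also reports means and SDs at each time point, a t test and correlations, so a later trial could be sized from the raw difference and SD.

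It is also fair to say that the absence of a correction is an inference from silence, as is the pooled SD on 22 degrees of freedom, and that anyone holding d and the group sizes can apply J afterwards. The plan is written in the past tense, but g needs only d and the degrees of freedom, so that does not prevent the change.

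What remains is narrow: for the quantity that the pilot is meant to supply, an estimator with no mean bias and lower mean squared error is available at almost no cost.

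**Conclusion.** The point holds as a minor, optional improvement. It does not invalidate the analysis. Under a pooled-SD, between-group d on 22 degrees of freedom with normal scores and equal variances, the average overstatement is about 3.6% of the true effect. The corresponding shortfall in a trial sized at the expected d is about 7%, which costs two to three percentage points of power at the assumed 80%.

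The percentages are secure given those assumptions. That the plan meets them is less certain, because it names neither the divisor nor the time point. The gain over d is real in mean bias and mean squared error but not in every respect, since the median of g falls slightly below the true effect.

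**What to change.** Replace the effect-size sentence with wording such as: *The effect size is Hedges' g = J × d, where d is the between-group mean difference divided by the pooled SD of the two groups and J = 1 − 3/(4 × df − 1), with df taken from the children actually analysed (J = 0.9655 at 22 df). It is reported with a 95% confidence interval, and g rather than d is carried into sample-size work for future studies.* The sentence should also name the assessment to which it applies. If the analysis is already done, the same statement can accompany the reported result.

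The cost is one sentence, one multiplication and an interval; no new data are needed. The downside is a point estimate about 3.5% less favourable, with a median slightly below the true effect. The interval matters more than the correction, because it shows a future planner how little 12 per arm can settle.
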